25. Female Subjects of childbearing potential, not using or not willing to continue using a medically reliable method of contraception for the entire trial duration, such as oral, injectable, or implantable contraceptives, or intrauterine contraceptive devices, unless they are surgically sterilized/hysterectomized or post-menopausal >1 year or who are not using any other method of contraception considered sufficiently reliable by the Investigator in individual cases.
26. Pregnancy, breast feeding, planned oocyte donation or oocyte implantation
27. Planned donation of germ cells, blood, organs or bone marrow during the course of the trial.
28. Participation in another clinical trial (use of investigational product or device) within 30 days preceding the baseline visit V0 or re-entry of Subjects previously enrolled in this trial (for exemption see Section 7.4).

29. Suspected inability to comply with trial procedures (e.g. repeated bronchoscopies, bronchial biopsy and sputum induction procedures, language problems, psychological disorders).
30. Suffering from any concomitant disease that might interfere with trial procedures or evaluations according to the Investigator's judgement.
31. Use of disallowed drugs.
32. Employee at the investigational site, relative or spouse of the Investigator.

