9.1.10 Contraception and Pregnancy Avoidance Procedure

From signing of informed consent, throughout the duration of the study, and for 30 days after last dose of study medication, female subjects of childbearing potential* who are sexually active with a nonsterilized male partner** must use adequate contraception. In addition they must be advised not to donate ova during this period.

*Females NOT of childbearing potential are defined as those who have been surgically sterilized (hysterectomy, bilateral oophorectomy or tubal ligation) or who are postmenopausal (eg, defined as at least greater than 12 months after last menstruation, confirmed before any study medication is implemented).

**Sterilized males should be at least 1 year postvasectomy and have confirmed that they have obtained documentation of the absence of sperm in the ejaculate.

An acceptable method of contraception is defined as one that has no higher than a 1% failure rate. The only acceptable methods of contraception are:

Barrier methods (each time the subject has intercourse):

- Male condom PLUS spermicide.
- Cap (plus spermicidal cream or jelly) PLUS male condom and spermicide.
- Diaphragm (plus spermicidal cream or jelly) PLUS male condom and spermicide.

Intrauterine devices (IUDs):

- Copper T PLUS condom or spermicide.
- Progesterone T PLUS condom or spermicide.

Hormonal contraceptives:

- Implants.
- Hormone shot/injection.
- Combined pill.
- Minipill.
- Patch.
- Vaginal ring PLUS male condom and spermicide.

Subjects will be provided with information on acceptable methods of contraception as part of the subject informed consent process and will be asked to sign a consent form stating that they understand the requirements for avoidance of pregnancy, donation of ova, during the course of the study.

During the course of the study, regular serum human chorionic gonadotropin (hCG) pregnancy tests will be performed only for women of childbearing potential and subjects will receive continued guidance with respect to the avoidance of pregnancy as part of the study procedures ([Appendix A](#)). Subjects must have a negative urine hCG pregnancy test at V2 prior to receiving first dose of investigational drug.

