 - c) that personal information (including personal health information) may be added to Takeda's research databases for purposes of developing a better understanding of the safety and effectiveness of the study medication(s), studying other therapies for patients, developing a better understanding of disease, and improving the efficiency of future clinical studies;
 - d) that subjects agree not to restrict the use and disclosure of their personal information (including personal health information) upon withdrawal from the study to the extent that the restricted use or disclosure of such information may impact the scientific integrity of the research; and

- e) that the subject's identity will remain confidential in the event that study results are published.
- 25. Female subjects of childbearing potential (eg, nonsterilized, premenopausal female subjects) who are sexually active must use adequate contraception (as defined in the informed consent) from Screening throughout the duration of the study. Regular pregnancy tests will be performed throughout the study for all female subjects of childbearing potential. If a subject is found to be pregnant during study, study medication will be discontinued and the investigator will offer the subject the choice to receive unblinded treatment information.
- 26. A statement that clinical trial information from this trial will be publicly disclosed in a publicly accessible website, such as ClinicalTrials.gov.

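### For women bound by Section 9.1.10, exclusion criterion 25 accepts contraception that 9.1.10 does not, and neither it nor consent element 25 states the 30 days after the last dose

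*Protocol*

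**What the plan says.** Three places in the protocol set the contraception rule.

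- **Section 7.2, exclusion 25.** A woman of childbearing potential is excluded if she is "not using or not willing to continue using a medically reliable method of contraception for the entire trial duration". The examples that follow are oral, injectable and implantable contraceptives and intrauterine devices, the last with no added method. A closing clause, awkwardly worded, lets in "any other method of contraception considered sufficiently reliable by the Investigator in individual cases". The criterion makes no distinction by sexual activity or partner and does not refer to Section 9.1.10.
- **Section 9.1.10.** The duty falls on women of childbearing potential "who are sexually active with a nonsterilized male partner". The standard is: "An acceptable method of contraception is defined as one that has no higher than a 1% failure rate". The list is closed: "The only acceptable methods of contraception are" those given there. For intrauterine devices it reads "Copper T PLUS condom or spermicide", and the progesterone device carries the same condition. The period starts at consent and runs "throughout the duration of the study, and for 30 days after last dose of study medication".
- **Appendix C, element 25.** Sexually active women of childbearing potential "must use adequate contraception (as defined in the informed consent) from Screening throughout the duration of the study". No period after the last dose is mentioned.

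**The concern.** Section 9.1.14 makes randomization depend on the inclusion and exclusion criteria. A woman bound by 9.1.10 who uses an intrauterine device alone, or a method outside the list that the investigator accepts, passes exclusion 25. From consent onward she does not meet 9.1.10, and Section 7.8 lists inadequate contraception as a category for withdrawal. The protocol thus admits her under one rule and finds her method unacceptable under another.

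The period matters for a second reason. Section 9.1.11 has pregnancies reported if they occur up to 30 days after the last active dose, so the protocol itself treats those days as exposure of interest. Appendix A schedules no pregnancy test after V6. In that window, protection rests on what the woman was told and agreed to, and two of the three places that state the rule do not state the 30 days.

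**Working it through.** No figure in the plan has to be reproduced. The check compares the texts and then sizes the period left uncovered.

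**1. Methods, for women bound by 9.1.10**

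| Method | Exclusion 25 | Section 9.1.10 |
|---|---|---|
| Oral, injectable, implantable | accepted | accepted |
| Intrauterine device, nothing added | accepted | not accepted |
| Intrauterine device with condom or spermicide | accepted | accepted |
| Unlisted method the investigator finds reliable | accepted | not accepted |

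The texts agree on the first and third rows and differ on the second and fourth. In both of those rows exclusion 25 is the looser text.

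**2. Period**

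Section 9.1.10 names the study period and the 30 days after the last dose as two separate parts. Exclusion 25 and consent element 25 name only the first. What is lost depends on when the trial is taken to end.

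*Reading A: the trial ends at the last visit.* In support, Section 6.1 gives a maximum total duration of 24 weeks, and Section 10.2.1.1 collects adverse events until V7. Section 9.3.6 places V7 within two weeks after V6. Under Appendix A, footnote a, V7 applies only after a second bronchoscopy. Let V7 fall k days after V6.

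- Last dose on the day of V6: uncovered days = 30 − k.
- Last dose on the day before V6: uncovered days = 30 − k − 1.

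| V7 | Last dose on V6 | Last dose the day before |
|---|---|---|
| Day 14 | 30 − 14 = 16 | 15 |
| Day 7 | 30 − 7 = 23 | 22 |
| No V7 (k = 0) | 30 | 29 |

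The count is lower if dosing stopped earlier than this. Cross-check on the nominal schedule, counted from V0: (6 + 16) × 7 + 30 = 184 days, against 24 × 7 = 168 days. The difference is 184 − 168 = 16 days, which matches the day-14 row.

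*Reading B: the trial includes the 30-day adverse-event follow-up.* Sections 2.0 and 6.1 list a safety follow-up of up to 30 days after the double-blind period among the trial periods. If that counts as trial duration and the last dose is at V6, the uncovered time is 30 − 30 = about 0 days.

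The range is therefore roughly 0 to 30 days. The 24-week maximum is not a firm end point either: Appendix A allows V6 a window of ±7 days, and Section 9.3.4 lets the biopsy be postponed by up to four weeks after an exacerbation.

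**The case against.** The strongest reply is that the two texts add up rather than collide. Exclusion 25 is an entry gate and 9.1.10 is a stricter duty from consent onward, so a site that applies both complies. Section 9.1.10 also requires that women be informed of the acceptable methods during consent and sign that they understand the requirements. A woman with an intrauterine device could then simply add a condom or spermicide. This stands, and a reader who infers that the two sections cannot both be followed goes too far. What remains is that exclusion 25 neither points to 9.1.10 nor says that 9.1.10 prevails. As an entry rule, it still accepts methods that 9.1.10 rules out.

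A reader might also infer that women are not told about the 30 days. The documents do not support that. The consent form is not shown, element 25 defers to what that form defines, and the consent sentence in 9.1.10 can be read as covering the requirements stated just before it. The finding is only that Appendix C, which sets the minimum content, does not call for the 30 days.

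A fixed gap of 16 days is likewise more than the text bears, because it rests on Reading A with V7 at day 14.

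Finally, it is tempting to say that women who are not sexually active, or whose partner is sterilized, are eligible anyway because 9.1.10 does not bind them. Exclusion 25 has no such qualifier. At present such a woman who uses none of the kinds of method it names enters only if the investigator accepts another one.

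**Conclusion.** Wrong as written: the protocol gives two different rules on which contraception is acceptable for the women whom 9.1.10 binds. The method conflict does not depend on any assumption about when the trial ends. It rests only on reading the awkward last clause of exclusion 25 in its evident sense, as accepting a method that the investigator approves. The missing 30 days are a second, softer inconsistency, worth roughly 0 to 30 days depending on the reading of trial duration and on V7.

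The severity is minor. This is a participant-safety wording point with no effect on endpoints, sample size or analysis. The number of women concerned is not given and cannot be computed; with entry at 40 to 80 years it is likely to be small.

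**What to change.** 1. **Exclusion 25, women bound by 9.1.10.** Replace the criterion's own method list and the discretion clause with a reference to the methods listed in 9.1.10, used from signing of consent, during the study and for 30 days following the final dose.
2. **Exclusion 25, other women of childbearing potential.** Keep the present handling, including the investigator's judgement, as a separate limb. Whether women with no need of contraception should enter freely is a decision for the sponsor, and this inconsistency does not force it.
3. **Appendix C, element 25.** Add the 30 days after the last dose of study medication.

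The cost is one reworded criterion, one added phrase, and a check that the consent form in use already states the 30 days. Item 1 tightens entry slightly for women using an unlisted method or an intrauterine device alone, but 9.1.10 already requires them to change or supplement that method. No data collection or analysis changes.

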7.3 Randomization Criteria

Subjects must meet all the following randomization criteria at V2 to be eligible for randomization into the double-blind treatment period (V2 = randomization visit):

1. No COPD exacerbation between V0 and V2 (as defined by the need for oral or parenteral glucocorticosteroid intake and/or hospitalization).
2. Tablet compliance $\geq 80\%$ and $\leq 125\%$.
3. The admission criteria at inclusion are still met.

Only Subjects who meet all randomization criteria will undergo the first bronchoscopy / bronchial biopsy.

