7.2 Exclusion Criteria

Subjects meeting any of the following criteria will be excluded from trial enrolment:

Criteria affecting the read-out parameters of the trial:

1. Clinical instability, defined as experiencing a COPD exacerbation six months prior to V0, as indicated by treatment with a systemically administered glucocorticosteroid and/or antibiotics and/or hospitalization.
2. An upper/lower respiratory tract infection e.g. common cold, sinus symptoms, pneumonia, which has not resolved four weeks prior to V0.

² Total pack years = No. cigarettes smoked per day/20 x no. years of smoking. For the purpose of the trial a former smoker is defined as a subject who has not smoked for ≥ 12 months at visit V0. Smoking status will be monitored throughout the trial but not verified by any objective tests.

3. Diagnosis of asthma and/or other relevant lung disease (e.g. history of primary or clinically significant bronchiectases, cystic fibrosis, bronchiolitis, lung resection, lung cancer, interstitial lung disease [e.g. fibrosis, silicosis, sarcoidosis], active tuberculosis) or previous episodes of pneumothorax.
4. Known alpha-1-antitrypsin deficiency.

Criteria within ethical considerations in terms of general health:

5. Duration of oxygen therapy ≥ 12 h/day.
(**GERMANY ONLY:** Any oxygen therapy at home.)
6. History of intubation for COPD or a respiratory failure of any cause in the past year.
7. Hypoxemia defined as oxyhemoglobin concentration $< 88\%$ when breathing room air measured by pulse oximetry.
8. Formal contraindications to sputum collection or impossibility to obtain a sample of sputum valid for analysis.
9. Clinically relevant abnormal laboratory values suggesting an undiagnosed disease requiring further clinical evaluation (as assessed by the Investigator).
10. Suspicion or diagnosis of a bleeding disorders irrespective of its pathophysiological mechanism: Thrombocytopenia (platelets $< 50000/\text{mL}$) and platelet dysfunction (e.g. uraemia), thrombotic or coagulation disorders and bleeding due to abnormal blood vessels (e.g. purpura simplex).
11. Severe psychiatric or neurological disorders.
12. History of depression associated with suicidal ideation or behaviour.
13. Hemodynamic instability (e.g. bradycardia with resting heart rate < 60 beats per min, tachycardia with resting heart rate ≥ 120 beats per min and/or a systolic blood pressure < 100 or > 180 mmHg).

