13a) (GERMANY ONLY: Hemodynamic instability (e.g. bradycardia with resting heart rate < 60 beats per min, tachycardia with resting heart rate ≥ 100 beats per min and/or systolic blood pressure < 100 or > 180 mmHg).)
14. History of increased intracranial pressure, superior vena cava obstruction, pulmonary hypertension, aneurysms and arteriovenous malformations within the lungs.
15. Congestive heart failure severity grade IV according to New York Heart Association Functional Classification (NYHA).
15a) (POLAND ONLY: Congestive heart failure severity grade III and IV according to New York Heart Association Functional Classification (NYHA).)

16. Haemodynamically significant cardiac arrhythmias or heart valve deformations.
17. History of angina pectoris (Class \geq II Canadian Cardiovascular Society Functional Classification of Angina Pectoris Scale) or a myocardial infarction within last 12 months, unless corrected with Percutaneous Transluminal Coronary Angioplasty (PTCA) or Coronary Artery Bypass Surgery (CABG) \geq 3 months prior to V0 and asymptomatic since then.
18. X-ray Computed Tomography (CT) or X-ray findings indicating a pulmonary disease other than COPD (e.g. tuberculosis, clinically significant bronchiectases, tumours). CT or X-ray results within 12 months prior to visit V0 are required.
 - 18a) (*GERMANY ONLY*: X-ray Computed Tomography (CT) or X-ray findings indicating an anomaly or pulmonary disease other than COPD (e.g. tuberculosis, clinically significant bronchiectases, tumours).)
19. Immunological diseases or known infection with Human Immunodeficiency Virus (HIV).
20. Liver impairment Child-Pugh B/C and/or active viral hepatitis.
21. Severe acute infectious diseases.
22. Any diagnosis of a malignant disease (other than basal or squamous cell carcinoma) within five years before enrolment into the trial.
23. Excessive alcohol intake or drug/substance abuse within the past year.
24. Any history of allergies, suspected hypersensitivity and/or contraindication to local anaesthetics (e.g. xylocaine, lignocaine) and/or sedative agents (e.g. benzodiazepines, propofol, opioids) that would not allow adequate anaesthesia and/or bronchoscopy sedation. Suspected hypersensitivity to the trial treatment (Roflumilast) or ingredients thereof, or any other contraindication for the use thereof.

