7.4 Re-Enrolment

Re-enrolment of Subjects is only allowed for subjects who failed screening or have to stop the study participation before randomization. After 4 weeks waiting time re-enrolment will be allowed once. However, Subjects who were withdrawn at visit V2 due to an exacerbation (moderate and/or severe exacerbation, and/or treated with antibiotics) between visits V0 and V2 may be re-enrolled after resolution of the exacerbation. If, during the second enrolment, the Subject again experiences such an exacerbation, the Subject must be withdrawn and no further re-enrolment is allowed.

In case a Subject is re-enrolled, the exclusion criteria nos. 1 and 28 do not apply. (see Section 7.2).

After having been randomized the Subject cannot be re-enrolled. For re-enrolled Subjects a new CRF has to be filled in starting at visit V0. A comment specifying that the Subject has been re-enrolled must be given on the screening log and in both CRFs.

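### The run-in exacerbation rule in 7.3 and 7.8 omits antibiotic-treated events that 7.2 and 7.4 count, leaving no clear fixed bar to randomization and baseline biopsy after a mild or resolved one on first enrolment

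*Protocol*

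**What the plan says.** Four places in the Protocol deal with exacerbations up to V2.

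- **7.2, exclusion 1**, under the label "Criteria affecting the read-out parameters of the trial", excludes an exacerbation in the six months before V0, "as indicated by treatment with a systemically administered glucocorticosteroid and/or antibiotics and/or hospitalization".
- **7.3, randomization criterion 1**, requires "No COPD exacerbation between V0 and V2 (as defined by the need for oral or parenteral glucocorticosteroid intake and/or hospitalization").
- **7.8, discontinuation criterion 1**, repeats the 7.3 definition for the same window.
- **7.4** says of subjects withdrawn at V2 for an exacerbation that those with a "moderate and/or severe exacerbation, and/or treated with antibiotics) between visits V0 and V2 may be re-enrolled after resolution of the exacerbation". If the same kind of event recurs during the second enrolment, withdrawal is mandatory.

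Randomization criterion 3 adds that the admission criteria must still hold at V2. Only subjects who meet all three criteria go on to the first bronchoscopy.

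**The concern.** One clinical event, an exacerbation treated with antibiotics alone, is handled in different ways. It excludes a subject if it falls before V0, and it forces withdrawal if it falls in the run-in of a second enrolment. In the run-in of a first enrolment, neither exacerbation criterion mentions it. 7.4 assumes that such subjects are withdrawn at V2, but no exacerbation rule in 7.3 or 7.8 withdraws them.

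The protocol itself treats these events as relevant to the read-out. Section 6.2 keeps out recent exacerbators so that bronchoscopy and sputum collection can be done safely. The V2 biopsy gives the baseline CD8+ density that enters the primary Poisson model (13.1.3.1). At stake are a baseline count taken soon after an airway event, and a bronchoscopy in a subject whom the design meant to be stable. Events late in run-in matter most.

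**Working it through.** **Step 1. The definitions side by side.**

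| Section | Window | Systemic steroid | Hospitalization | Antibiotics |
|---|---|---|---|---|
| 7.2 exclusion 1 | six months before V0 | yes | yes | yes |
| 7.3 criterion 1 | V0 to V2 | yes | yes | no |
| 7.8 discontinuation 1 | V0 to V2 | yes | yes | no |
| 7.4 re-enrolment | V0 to V2 | not itemized (moderate/severe) | not itemized (moderate/severe) | yes |

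**Step 2. Does another rule stop the subject?** Take a first-enrolment subject with an antibiotic-only exacerbation after V0 that is non-severe, or resolved by V2.

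- *Criterion 3 with exclusion 1.* The exclusion looks back from V0, and the event comes after V0. If it were silently moved to V2, criterion 1 would be redundant on first enrolment.
- *Criterion 3 with exclusion 2.* This concerns a respiratory infection "which has not resolved four weeks prior to V0". It is also tied to V0, though its reach is arguable (see the objection).
- *Excluded medications (7.6).* Antibiotics are not listed; systemic steroids are. 7.7 allows drugs for concurrent diseases but asks for constant dosage, so it neither clearly permits nor bans a short course.
- *Severity limits.* The FEV1 limits, exclusion 7 ("Hypoxemia defined as oxyhemoglobin concentration" below 88%) and exclusion 21 ("Severe acute infectious diseases") stop subjects who are clearly ill, not those with a mild or resolved event.
- *Judgement.* Exclusion 30 ("Suffering from any concomitant disease that might interfere with trial procedures or evaluations"), the harm and lung-function items in 7.8, and the deferral in Appendix F all depend on the investigator.
- *Postponement after exacerbation (9.3.4).* This applies only between V2 and V6.

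No clear fixed bar remains.

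**Step 3. Minimum interval before the V2 biopsy.** Inputs: V2 is at six weeks, -3/+5 days (Appendix A), so the earliest V2 is 42 - 3 = 39 days after V0 and the latest is 42 + 5 = 47. Six months is taken as 183 days. Exclusion 2 requires four weeks, or 28 days, since resolution.

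| Event | Calculation | Minimum |
|---|---|---|
| Before V0, first enrolment | 183 + 39 | about 222 days |
| In run-in, withdrawn and re-enrolled, not a respiratory infection | 0 + 39 | 39 days after resolution |
| In run-in, withdrawn and re-enrolled, a respiratory infection | 28 + 39 | 67 days after resolution |
| In run-in, first enrolment, not withdrawn | none | 0 days (range 0 to 47) |

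The third row follows because 7.4 waives only exclusions 1 and 28 on re-enrolment, so exclusion 2 still applies at the new V0. The re-enrolment rows count from resolution and the other two from the event. These are the protocol's own intervals and do not measure harm.

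**Step 4. Would the described analysis sets show it?** Major violations for the valid cases set come from the inclusion, randomization and read-out criteria (13.1.1.4). On the V0-anchored reading, the event breaches none of them. The exacerbation-free subset of the full analysis set (13.1.3.2) concerns double-blind treatment only.

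**The case against.** The strongest objection is that criterion 3 already does the work. Section 7.0 requires all entry criteria to be confirmed before randomization, and 9.1.14 admits only subjects who meet no exclusion criterion. Re-read at V2, an infection that began in run-in had, literally, not resolved four weeks before V0, so exclusion 2 could be said to catch it. This reading is possible and would cover many infective exacerbations. It is not the natural sense of a criterion dated to V0, and it does not reach antibiotic use without a respiratory infection. It makes the gap less certain without removing it, and on that reading the valid cases set would also register the event.

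A second objection is that 7.4 gives permission to re-enrol and does not itself order withdrawal on first enrolment. The withdrawals it mentions could come from investigator judgement under 7.8, and the identical wording of 7.3 and 7.8 could be a deliberate threshold. That is fair for first enrolment. It does not explain why the same event then compels withdrawal on second enrolment.

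Third, the consequence is limited. The event precedes randomization, so it is balanced between arms in expectation, and 9.3.4 also relies on investigator judgement about stability before the V6 biopsy. This stands.

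A reader might infer that every subject given antibiotics in run-in will be randomized, or that the treatment comparison is biased. The documents support neither: investigators can stop subjects, and no event rate or CD8+ shift is given. Nor does it follow that the analysis cannot find such subjects, since the blinded data review and an SAP that is not at hand may identify them.

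**Conclusion.** The inconsistency is real: two operative criteria omit a component that two related sections include. For a first-enrolment subject with a non-severe or resolved antibiotic-only exacerbation in run-in, the text sets no clear fixed bar to randomization and no minimum interval before the baseline biopsy. The comparable minimum is about 222 days for an event before V0, and 39 or 67 days after resolution on re-enrolment.

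The conclusion rests on reading exclusions 1 and 2 as tied to V0, which fits their wording but can be contested for exclusion 2. The effect on the baseline covariate and on bronchoscopy safety is likely modest and cannot be quantified from the documents. Severity is low to moderate, and confidence is moderate.

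**What to change.** In 7.3 criterion 1 and 7.8 discontinuation criterion 1, add *and/or antibiotics* to the treatments that define the exacerbation, matching exclusion 1 and 7.4. Sites then have one definition, 7.4 has a rule to refer to, and nothing depends on how exclusion 2 is read at V2.

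The cost is two short insertions, no new procedures, and a few more run-in failures, who may re-enrol once under 7.4 after resolution. Deleting the antibiotic phrase from 7.4 would also reconcile 7.4 with 7.3 and 7.8, but it would leave late run-in events eligible for the baseline biopsy.
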